9.4 Reporting Procedures

9.4.1 General

All adverse events will be captured on the appropriate study-specific case report forms (CRFs). In addition, all serious adverse events, regardless of causality to study drug, will be reported promptly to the Principal Investigator and Study Coordinator.

9.4.2 Institutional Review Board

All adverse events and serious adverse events will be reported to the IRB per current institutional standards. If an adverse event requires modification of the study protocol and informed consent, these modifications will be provided to the IRB with the report of the adverse event or as soon as possible thereafter.

9.4.3 Food and Drug Administration (FDA)

In this trial using a medication for an FDA-approved indication, unexpected adverse events believed to be definitely, probably, or possibly related to the medication (s) will be reported to the Food and Drug Administration via Med Watch (using the online form available at <https://www.accessdata.fda.gov/scripts/medwatch/>; by telephone [name]; or by fax [name] using form available at <http://www.fda.gov/medwatch/report/hcp.htm>). This reporting mechanism will be used to report events that may be related to the use of the ropivacaine.

9.5 Data and Safety Monitoring

This is a DSMP Level I study under the SKCCC Data Safety Monitoring Plan. The Clinical Research Office QA Group will perform an audit at the end of the first year and then periodically depending on the rate of accrual and prior audit results. The SKCCC Safety Monitoring Committee will review all trial monitoring and reporting annually. The PI will be responsible for monitoring the study. The study's data will be continuously reviewed to assure its validity. The PI will constantly review the safety reports to confirm that the safety outcomes favor continuation of the study. Additionally, the PI will be responsible for maintaining the clinical protocol, monitoring clinical trial efficacy endpoints, reporting adverse events, assuring that consent is obtained and documented, reporting of unexpected outcomes, and reporting the status of the trial in the continuing renewal report submitted to the IRB and to the trial monitoring review group.

Content of the continuing renewal report at a minimum will include year-to-date and full trial data on: accrual and eligibility, protocol compliance, treatment administration, toxicity and ADR reports, response, survival, regulatory compliance and compliance with prearranged statistical goals. The report will be submitted in a timely manner according to the schedule defined by Johns Hopkins Medicine Institutional Review Board.

9.6 Data Management

All information will be collected on study-specific case report forms (CRFs) by study staff. The Principal Investigator as well as the Sidney Kimmel Comprehensive Cancer Center Clinical Research Office will review these data for completeness and accuracy.

9.7 Safety Meetings

Scheduled meetings will take place as needed and will include the protocol principal investigator, study coordinator(s), sub-investigators (as appropriate), and biostatisticians (as appropriate) involved with the conduct of the protocol. During these meetings matters related to the following will be discussed: safety of protocol participants, validity and integrity of the data, enrollment rate relative to expectation, characteristics of participants, retention of participants,

adherence to the protocol (i.e., potential or real protocol deviations/violations), completeness of data collection, and progress of data analysis.

9.8 Monitoring

The principal investigator will have sole responsibility for monitoring and oversight of problems/events related to this research.

10. Statistical Considerations

This study is a randomized controlled trial based on the bilateral mastectomy followed by bilateral immediate tissue expander breast reconstruction surgical protocol currently in use at Johns Hopkins.

Patients will be randomized 1:1 to either 0.5% ropivacaine pre-operatively placed paravertebral blocks or subcutaneous paravertebral saline (placebo) injections. Using two pain scales, the Patient Pain Assessment Questionnaire (Appendix A) and Subjective Pain Survey (Appendix B), the post-operative pain will be compared between treatment and control groups. Differences in opioids use between groups at different time points will also be assessed as a more objective measure of post-operative pain.

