5.1 Summary of Study Design

Participants meeting inclusion criteria will be enrolled and baseline data collection completed prior to randomization and surgery. Baseline data collection includes a general patient history, the Patient Pain Assessment Questionnaire which includes static and moving pain scores as well as nausea and sleep interference scores (Appendix A), the Subjective Pain Survey (Appendix B), the pre-operative Breast-Q (Appendix C), the RAND-36 (Appendix E), and the Quick DASH survey (Appendix F).

Patients will be randomized 1:1 to ropivacaine- (treatment) pre-operatively placed paravertebral blocks or subcutaneous paravertebral saline (placebo) injections in a double-blinded design. Neither the treatment team (the anesthesiologist and the surgeon) nor the patient will know the randomization assignment. The pharmacy will be unmasked.

Patient-specific surgical details will be recorded intraoperatively. Following the surgery, post-operative pain [(measured by the Patient Pain Assessment Questionnaire (Appendix A)], pain medication/opioid use, and the occurrence of adverse events (AEs)/serious adverse events (SAEs) will be assessed routinely by staff during the hospital stay and on Days 2 and 3 by telephone interview with study staff for discharged patients. The typical post-operative length of hospital stay is approximately one day. Participants are to return to clinic for the Day 7 (± 2 days) follow-up visit. At this visit an updated medical history will be completed, pain medication/opioid use recorded, and participant AEs/SAEs assessed. Additionally, participants will complete the following questionnaires: Patient Pain Assessment, RAND-36, and Quick DASH.

Long-term quality-of-life/health outcomes assessments will be done on post-operative Day 90 (± 14 days), Year 2 (± 14 days), and Year 4 (± 14 days). During the Day 90 visit, pain scores (Patient Pain Assessment Questionnaire), pain medication/opioid use, post-operative Breast-Q, RAND-36, and the Quick DASH will be administered. The Year 2 and Year 4 follow-ups are included as tertiary endpoints to capture differences in chronic pain, and patients will be asked to complete the same questionnaires as at the Day 90 follow up.

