5.2.2 Exclusion Criteria

Participants with the following conditions will be ineligible:

- Any concurrent opioid analgesic use (baseline opioid use must be 0 to be eligible).
- Liver dysfunction and/ or cirrhosis.

- Renal insufficiency, with creatinine greater than 1.5 mg/mL.
- Patients weighing less than 50 Kg.
- Concurrent use of the SSRI antidepressant fluvoxamine (Luvox).

Having a tattoo on the back that is too large to permit PVB injections (as determined by the provider performing the procedure).

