5.11 Duration of Study Participation

Study participation continues through Year 4 post-operatively. However, the majority of data collection will occur during the first 7 days after the participant’s immediate tissue expander reconstruction following mastectomy. An additional study visit will occur in clinic at Day 90 (± 14 days), prior to the participant’s undergoing any additional reconstructive breast surgery procedures. Thereafter, follow-up phone interviews will occur at post-operative Year 2 (± 14 days), and post-operative Year 4 (± 14 days).

Participants are to return to clinic for a Day 90 (± 14 days) follow-up visit. To encourage participation, participant parking and a \$15 gift card will be given (or mailed) to participants who complete the Day 90 visit.

If a participant chooses to withdraw, is withdrawn, or refuses to participate through Day 90, all efforts will be made to collect all Day 90 post-operative data at the time of study withdrawal. Reasons for premature participation/treatment withdrawal will be recorded to the best of the study team’s ability. Reasons for early withdrawal may include the following:

1. Unanticipated or serious adverse events.
2. Inter-current illness that prevents further administration of treatment or would affect assessment of clinical status to a significant degree.
3. Subject becomes pregnant.
4. Subject refuses to continue treatment.
5. Any reason the study physician deems it necessary for the benefit of the participant.
6. Subject is lost to follow-up.

6. Study Calendar

Table 3. Calendar of study events/procedures.

Parameter	Pre-Study	Surgery (Day 0)	Day1	Day 2*	Day 3*	Day 7 (± 2 days)	Day 90 (± 14 days)	Post-Op Years 2 & 4 (± 14 days)
General Patient History Form	X							
Update Medical History		X	X			X	X	X
Treatment administration (Ropivacaine/Placebo)		X						
Intra-Operative Case report Form (CRF)		X						
Adverse Events of Interest/SAE Assessment		X	X	X	X	X	X	
Pain Meds/Opioid Use	X		X	X	X	X	X	
Questionnaires								
Patient Pain Assessment Questionnaire	X		X	X	X	X	X	X

Subjective Pain Survey	X							
BREAST-Q [®] , Pre-Op	X							
BREAST-Q [®] , Post-Op							X	X
RAND-36 Questionnaire	X					X	X	X
Quick DASH Questionnaire	X					X	X	X

Note: Additional tests may be performed at the discretion of the treating investigator as clinically indicated.

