10.1 Objectives

10.1.1 Primary Objective

To determine if post-operative static pain scores differ between women undergoing bilateral mastectomy followed by bilateral immediate tissue expander reconstruction randomized either to ropivacaine- (treatment) pre-operatively placed paravertebral blocks or subcutaneous paravertebral saline (placebo) injections.

Post-operative pain scores will be measured by a 0-10 Likert scale 6 hours after the end of surgery while the patient is still hospitalized (post-operative day 0). This will be patient-provided data. Unblinded data analysis will compare scores between treatment and control groups.

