Appendix B: Subjective Pain Survey

Subject Number: _____ **Study Personnel:** _____

Last Name: _____ **First Name:** _____

MRN: _____ **DOB:** _____ **Date:** ___/___/___ **Time:** _____

Thank you for participating in this study. After reading each question, please circle the number in the box that best describes your situation. If you are unsure how to answer a question, choose the answer that comes closest to how you feel. Please answer all questions.

On a scale of 1 to 5, please indicate how painful you believe these scenarios are:

	Not painful at all	A little painful	Somewhat painful	Quite painful	Extremel y painful
a. Biting one's tongue?	1	2	3	4	5
b. An average toothache?	1	2	3	4	5
c. Burning one's hand on a stove?	1	2	3	4	5
d. Badly spraining one's ankle?	1	2	3	4	5
e. Average migraine headache?	1	2	3	4	5
f. Receiving an intramuscular injection?	1	2	3	4	5
g. Stubbing one's toe really hard?	1	2	3	4	5
h. The initial pain from a bee sting?	1	2	3	4	5

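### Minor: Section 10 compares post-operative pain on a survey given only before surgery; correct the sentence and, as a cheap improvement, use one baseline-adjusted estimate for 6-hour static pain

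*Combined protocol and SAP*

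**What the plan says.** The opening of Section 10 names two instruments for the between-arm comparison of pain after surgery: "Using two pain scales, the Patient Pain Assessment Questionnaire (Appendix A) and Subjective Pain Survey (Appendix B), the post-operative pain will be compared".

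Section 5.1 places the Subjective Pain Survey among the baseline forms. It names Appendix A as the post-operative pain instrument. At Day 7, "participants will complete the following questionnaires: Patient Pain Assessment, RAND-36, and Quick DASH". At Day 90, "pain scores (Patient Pain Assessment Questionnaire), pain medication/opioid use, post-operative Breast-Q, RAND-36, and the Quick DASH will be administered", and Years 2 and 4 repeat the Day 90 set. In Table 3 the row "Subjective Pain Survey" has one mark, under Pre-Study. Appendix B itself reads: "On a scale of 1 to 5, please indicate how painful you believe these scenarios are".

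On the use of baseline, Section 5.1 states: "Baseline data collection includes a general patient history, the Patient Pain Assessment Questionnaire which includes static and moving pain scores". Section 10.2 computes differences from baseline for every outcome and compares them, like the raw scores, by t-test or rank sum test according to distribution. It names no model with the pre-operative score as a covariate. The primary measure is in Section 10.1.1: "Post-operative pain scores will be measured by a 0-10 Likert scale 6 hours after the end of surgery".

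For the final analysis, Section 10.2 sets p below 0.05 for the primary outcome. Section 10.4 specifies the Wilcoxon test, giving the small numbers at the two interim looks as the reason. Its Table 5 lists critical Z values of 3.36, 2.68 and 1.98, derived for that test.

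**The concern.** As written, Section 10 promises a comparison for which no data will exist. A later reader could take its absence from the report for an unreported outcome.

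The second matter is one of efficiency. A change score subtracts the whole baseline value whatever its correlation with the outcome. If that correlation is low, subtraction can add noise. ANCOVA uses the same two measurements and lets the data set the weight. What is at stake is the width of a supportive confidence interval, not the validity of the primary test.

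**Working it through.** **1. The survey.** After Pre-Study, Table 3 has seven columns: Day 0, Days 1, 2, 3, 7 and 90, and Years 2 and 4 together. The survey is marked in 0 of the 7; Appendix A is marked in 6 of the 7 (not Day 0). The prose of Section 5.1 agrees, so a damaged table does not explain the gap. Appendix B has eight items on hypothetical events and none on the patient's own pain, so giving it after surgery would not rescue the sentence.

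**2. The plan's own figure.** No figure depends on the survey. Inputs for the adjusted estimate are the difference of 1.5, SD 2.5, two-sided 0.05 and 70 patients (Section 10.3), and the 35:35 split (Section 1). The stated 90% power does not reproduce: 35 per arm gives 70.9% by the normal approximation and 69.7% by noncentral t. That is a separate matter, noted here only because adjustment does not mend it.

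**3. Half-widths of the 95% CI, fixed-sample normal model.** R is the correlation of pre-operative with 6-hour static pain and S is the baseline SD. The documents give neither, so both are assumed over a range.

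- Unadjusted: t(68) × 2.5 × sqrt(2/35) = 1.9955 × 0.5976 = 1.193.
- ANCOVA: t(67) × 2.5 × sqrt(1 − R²) × sqrt(2/35) × sqrt(1 + 1/66) = 1.202 × sqrt(1 − R²).
- Change score: t(68) × sqrt(2.5² + S² − 2 × R × 2.5 × S) × sqrt(2/35).

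| R | ANCOVA half-width | Against 1.193 | Power at 1.5 (unadjusted 69.7%) |
|---|---|---|---|
| 0 | 1.202 | 0.8% wider | 69.0% |
| 0.2 | 1.178 | 1.3% narrower | 70.7% |
| 0.3 | 1.146 | 3.9% narrower | 73.0% |
| 0.5 | 1.041 | 12.7% narrower | 80.9% |

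ANCOVA breaks even with the unadjusted estimate at R = sqrt(1/67) = 0.12. By the normal approximation, 90% power would need R of about 0.63.

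Change score at R = 0.2:

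- S = 1.0: variance 6.25 + 1.00 − 1.00 = 6.25, half-width 1.193.
- S = 2.5: variance 6.25 + 6.25 − 2.50 = 10.00, half-width 1.508.

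The change score loses to the unadjusted score whenever S exceeds 2 × R × 2.5 = 5R, which is 1.0 here. Below that it does not lose. At S = 0.5 the variance is 6.25 + 0.25 − 0.50 = 6.00 and the half-width 1.168, slightly below ANCOVA's 1.178.

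**4. Thresholds.** Two-sided nominal p for the Table 5 values is 2 × (1 − Φ(Z)): 0.00078, 0.0074 and 0.0477. The alpha column of Table 5 (0.00079, 0.0076, 0.05) matches the cumulative error spent, so its last entry is not the p-value at Z = 1.98. Read as an ANCOVA t, 3.36 on 25 df is p = 0.0025 and 1.98 on 67 df is p = 0.0518. The Table 5 values therefore do not transfer to ANCOVA.

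**The case against.** The strongest reply is that little turns on this. The survey sentence is a slip in an introductory paragraph, and the ANCOVA is a preference about a supportive analysis. Both points stand, and they are why the matter is minor. Deletion is also not the only remedy: stating a baseline role for the survey resolves the conflict equally well.

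A reader might infer more than the documents support:

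- **That the primary comparison is compromised.** It is not. The survey appears in no objective, endpoint or sample-size statement, and the unadjusted test is valid.
- **That baseline pain goes unused.** Section 10.2 uses it through change scores and also mentions longitudinal methods. What is missing is a covariate role. The visits that Section 10.2 lists start at Day 1, so its reach to the 6-hour score rests on its applying to every outcome.
- **That adjustment would recover the stated power.** It would not at any plausible R. Eligibility requires that "baseline opioid use must be 0 to be eligible", so pre-operative pain may sit near zero and R may be low.
- **That Wilcoxon at all three looks is already settled.** Section 10.2 still allows a t-test at the end. Choosing one test resolves an ambiguity; it does not simply keep an existing rule.

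One practical objection also stands. Item 9 of Appendix A has eight interference ratings and no composite rule, while Section 10.1.1 describes only a 0-10 scale. A common scoring rule must exist before any adjustment. Table 3 shows no Appendix A form on Day 0, although Section 5.1 has staff assessing pain with it throughout the hospital stay, which may cover the 6-hour score.

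**Conclusion.** The contradiction is certain and minor: the comparison on the Subjective Pain Survey cannot be made, and correcting the sentence changes no endpoint, sample size, power or alpha figure.

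The adjusted estimate is an optional improvement. Its effect on the interval runs from 0.8% wider at R = 0 to 12.7% narrower at R = 0.5, with the lower part of that range more plausible. The advantage over change scores is clear if baseline scores vary widely and disappears if they barely vary. These sizes rest on a fixed-sample normal model, 35 per arm, SD 2.5, and assumed values of R and the baseline SD.

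The final-analysis rule is ambiguous between Sections 10.2 and 10.4. The gap in threshold is small (0.05 against 0.0477), but the choice of test is open too.

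**What to change.** 1. **Section 10, opening.** Remove the Subjective Pain Survey from the sentence on comparing post-operative pain and describe it as a baseline measure. Cost: one sentence.

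2. **Section 10.2, optional.** For 6-hour static pain only, replace the change-from-baseline comparison with one supportive ANCOVA: arm plus pre-operative static pain, reported as a mean difference with 95% CI. State one scoring rule for static pain and use it at both times. Fill missing baseline values with the pooled mean, ignoring arm. Fix this before the 28-patient look. The ANCOVA should drive no stopping or success decision, and its t should not be read against the Table 5 Z values. Cost: one paragraph, one degree of freedom, and an interval about 0.8% wider if R is near 0. The pre-operative form is already scheduled.

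3. **Sections 10.2 and 10.4.** Name one test and one threshold for the final analysis. If Table 5 governs, that is the Wilcoxon test at a critical Z of 1.98 (nominal p 0.0477), replacing both the t-test option and p below 0.05 for this outcome. Present it as a decision. Cost: one sentence in each section; the Table 5 boundaries do not change.

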10.1 Objectives

10.1.1 Primary Objective

To determine if post-operative static pain scores differ between women undergoing bilateral mastectomy followed by bilateral immediate tissue expander reconstruction randomized either to ropivacaine- (treatment) pre-operatively placed paravertebral blocks or subcutaneous paravertebral saline (placebo) injections.

Post-operative pain scores will be measured by a 0-10 Likert scale 6 hours after the end of surgery while the patient is still hospitalized (post-operative day 0). This will be patient-provided data. Unblinded data analysis will compare scores between treatment and control groups.

10.1.2 Secondary Objectives

To determine if post-operative moving pain scores, opioids use, nausea, and sleep interference differ between women undergoing bilateral mastectomy followed by bilateral immediate tissue expander reconstruction randomized either to ropivacaine- (treatment) pre-operatively placed paravertebral blocks or subcutaneous paravertebral saline (placebo) injections.

Pain score, opioids use, nausea, and sleep interference data will be collected via patient self-report. When possible (i.e., while hospitalized) objective data on opioids and other pain medication administered to the patient will be used.

10.1.3 Tertiary Objectives

To determine if long-term changes in Quality of Life scores [the RAND-36 Health Survey, Disability of the Arm, Shoulder, and Hand (Quick DASH) questionnaire, and Breast-Q scores] differ between women undergoing bilateral mastectomy followed by bilateral immediate tissue expander reconstruction randomized either to ropivacaine- (treatment) pre-operatively placed paravertebral blocks or subcutaneous paravertebral saline (placebo) injections.

This data will be collected via validated questionnaires through patient interviews at 3-months, 2-years, and 4-years (± 14 days) after surgery.

Once enrolled in the study, participants will be encouraged to remain in the study for the 4 years following surgery in order to get final pain scores and quality-of-life/health outcome survey information. Participants who cannot be contacted after several phone attempts and the sending of 2 certified letters via US Postal Service for 3-month, 2-year, and/or 4-year outcome assessments will be considered lost to follow-up.

10.2 Study Design

Descriptive statistics for all outcome data (primary, secondary, and tertiary) will be calculated for each treatment group (ropivacaine or placebo), for each time point (days 1-3, day 90, year 2 and year 4). Student's t-test or Wilcoxon rank sum test will be used to compare the 2 treatment groups with regards to continuous or ordinal (approximately continuous) data, based on the distribution of the values (normally distributed or not normally distributed). Also change from baseline to each time point (follow-up) will be calculated for each outcome. The distributions of these "change values" will be analyzed in the same manner (depending on distribution). P-values less than 0.05 will be considered statistically significant for the primary outcome.

Longitudinal methods will be used to examine trends in scores, and changes in scores over time.

Opioid use also will be analyzed. IV morphine delivered via a Patient Controlled Analgesia pump during the first 24 hours of post-operative hospitalization will be recorded. Oxycodone and Tylenol taken by the patient after the first 24 hours until post-operative day seven will be recorded by the patient unless the patient is still hospitalized, in which case it will be recorded in the patient's medical record and abstracted by study staff. Answers to pain questionnaires and information regarding analgesic use will be verified by daily telephone calls to the patients by study staff. A common "pain unit" will be developed to standardize the various methods of opioid administration. Survival analyses will be used to compare time to opioid use, and time to stopping of opioid use. Descriptive statistics will be used to quantify amount and timing of opioid use, as well as proportion of patients requiring opioids post-operatively.

Furthermore, we will use the DASH survey, BREAST-Q[®], and the RAND-36 to determine the amount of functional long-term differences (3 months, 2 and 4 years after surgery) between treatment groups. These surveys will be used to compare the functional use of the arm before surgery to its use three months after mastectomy with immediate reconstruction.

Adverse events will be quantified and proportions of patients in each treatment group with different specific types of adverse events will be compared for safety data. Chi Square tests or Fisher's Exact Tests will be used to compare the proportions of patients with adverse events.

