10.3 Sample Size and Accrual

We expect that it will take 24 months to collect data on all patients through Day 90. Assuming a placebo effect of 30%, we would anticipate a true difference of 1.5 VAS units between the two groups. A true difference between scores of 4.1 to 2.6 would be clinically significant since it would bring a patient from the "moderate" down into the "mild" pain category. Thus a total of 70 patients will enter this placebo-control parallel-design study. The probability is 90 percent that the study will detect a treatment difference at a two-sided 0.05 significance level. This is based on the assumption that the standard deviation of the response variable is 2.5.

10.4 Interim Analyses for Efficacy.

A total of two interim analyses for efficacy will occur after the enrollment of 28 (40%) and 42 (60%) patients, giving a total of 3 'looks' at the data including the final analysis at 70 patients enrolled. Because of the small sample size in the first and second interim analyses, we will test for the equality of static pain scores at 6 hours post-surgery by treatment group using the Wilcoxon rank sum test. This statistical test considers the rank of the pain scores without regard to the distribution of these outcome measures; however, the test of significance uses a Z-score, which has a standard normal distribution.

In order to control for the overall type I error for the three proposed analyses, we will use a group sequential approach that utilizes the O'Brien-Fleming (1979)²⁷ alpha spending function. The critical Z-values for the Wilcoxon rank sum test assuming O'Brien-Fleming boundaries were determined by the STATA command 'landemets', which calculates these boundaries following the method of Lan and DeMets (1983)²⁸. Table X below gives the critical Z values and corresponding alpha levels at each analysis required to reject the null hypotheses of equality of pain scores by treatment group. In this null hypothesis, we consider a two-sided test which makes no assumption about the direction of the effect (e.g. placebo patients could potentially have a lower mean pain score than those on the intervention).

Table 5: Critical Z values and corresponding alpha levels for test the null hypothesis that static 6 hour post-surgery pain scores are equal among treatment groups.

Analysis number	Proportion of total N	critical Z to reject H0	Alpha(i) level
1	0.4	3.36	0.00079
2	0.6	2.68	0.0076
3	1.0	1.98	0.05

References

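### The final primary test and its threshold are not fixed: section 10.2 allows a t-test or Wilcoxon at p<0.05, while section 10.4 and Table 5 give a Wilcoxon Z boundary of 1.98

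*Combined protocol and SAP*

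**What the plan says.** Section 10.2 (Study Design) covers primary, secondary and tertiary outcomes together. For continuous or near-continuous data, "t-test or Wilcoxon rank sum test will be used to compare the 2 treatment groups", the choice being made "based on the distribution of the values (normally distributed or not normally distributed". It names no normality test and no cut-off. It does not say whether pooled values, each arm or residuals are inspected. The same paragraph adds: "P-values less than 0.05 will be considered statistically significant for the primary outcome".

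Section 10.4 (Interim Analyses for Efficacy) deals with static pain at 6 hours. It plans three looks: "A total of two interim analyses for efficacy will occur after the enrollment of 28 (40%) and 42 (60%) patients", with the final analysis at 70. It explains its choice of test this way: "Because of the small sample size in the first and second interim analyses, we will test for the equality of static pain scores", using the Wilcoxon rank sum test. On the boundaries it says: "The critical Z-values for the Wilcoxon rank sum test assuming O'Brien-Fleming boundaries were determined by the STATA command" landemets. Table 5 is introduced as giving critical Z values and "corresponding alpha levels at each analysis required to reject the null hypotheses of equality of pain scores by treatment group". Its rows are 3.36, 2.68 and 1.98, so the final look is included.

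**The concern.** The test that decides a trial should be settled before the data are seen. Under 10.2 it is not: the final comparison may be either test, depending on a judgement for which no rule is given. The stated reason for Wilcoxon in 10.4, small numbers at the interims, does not carry over to the final analysis, although the final boundary is labelled as a Wilcoxon value.

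The threshold is unsettled too. A final p-value between 0.0477 (the nominal level of Z = 1.98) and 0.05 is significant under 10.2 and not significant under Table 5.

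At stake is the verdict when the result is close. Two competent analysts could follow the document and run different primary tests, and nothing in it would show which was intended.

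**Working it through.** **1. Reproduce Table 5.** Inputs from 10.4: information fractions 0.4, 0.6 and 1.0; two-sided 0.05; O'Brien-Fleming-type Lan-DeMets spending. With 0.025 per side, cumulative spending is 2[1 − Φ(2.2414/√t)].

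- t = 0.4: 2.2414/0.6325 = 3.544; 0.000394 per side, 0.00079 two-sided.
- t = 0.6: 2.2414/0.7746 = 2.894; 0.00381 per side, 0.0076 two-sided.
- t = 1.0: 0.025 per side, 0.05 two-sided.

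Solving for the boundaries gives Z = 3.357, 2.680 and 1.981. The table is right, and its alpha column is cumulative.

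**2. The two final thresholds.** Nominal p for 1.98 is 2[1 − Φ(1.98)] = 0.0477. Using 3.36, 2.68 and 1.98 gives overall alpha 0.0502; using 1.96 at the end gives 0.0524. If a raw t on 68 df is compared with 1.98, its nominal p is 0.0518; the t cut-off matching Z = 1.98 is 2.016. These differences are small.

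**3. How close to the boundary results may fall.** Section 10.3 gives a difference of 1.5 and SD 2.5, with 35 per arm. Expected Z = 1.5/(2.5 × √(2/35)) = 1.5/0.598 = 2.51, about half a standard error above 1.98. Results near the boundary are plausible.

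**4. How often the tests disagree.** The documents give no score shape, so three were assumed: normal; normal rounded and clipped to whole numbers 0-10; and skewed (beta-shaped) whole numbers 0-10. Means were 4.1 and 2.6, SD 2.5, 35 per arm, 40,000 trials. A single final look compared Wilcoxon at |Z| ≥ 1.98 with the t-test at p ≤ 0.0477.

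| Assumed shape | Wilcoxon rejects | t-test rejects | Disagree, design effect | Disagree, null |
|---|---|---|---|---|
| Normal | 66.6% | 68.9% | 6.5% | 1.9% |
| Rounded 0-10 | 65.7% | 67.2% | 5.0% | 1.5% |
| Skewed 0-10 | 75.0% | 68.5% | 7.5% | 1.1% to 2.6% |

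A separate run with beta-binomial scores, both tests at p<0.05, gave 6.3% disagreement at the design effect.

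**5. What a rule fixed in advance would do.** Two Shapiro-Wilk rules were tried, one applied to each arm and one to residuals (both are assumptions; 8,000 trials each). Compared with always using Wilcoxon at the design effect, the verdict changed in 0.6% to 1.4% of trials for rounded scores, about 0% for skewed scores, and 5% to 6% for continuous normal data. Type I error was 0.046 to 0.050; a further simulation gave 0.049 to 0.055, close to either test alone. The two rules often select differently: for rounded scores at the design effect, the per-arm rule chose the t-test in 11% of trials and the residual rule in 43%, and they chose different tests in 37%.

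**6. Type I error over all three looks** (Wilcoxon interims at 14 and 21 per arm, 100,000 trials).

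| Final analysis | Overall two-sided type I error |
|---|---|
| Wilcoxon fixed, Z 1.98 | 0.048 to 0.050 |
| t-test fixed, p ≤ 0.0477 | 0.049 to 0.051 |
| Whichever is significant, Table 5 level | 0.054 to 0.063 |
| Whichever is significant, p<0.05 | 0.056 to 0.066 |

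**The case against.** The best defence is that 10.4 already answers the question. It is the section specific to 6-hour static pain, and it labels every Table 5 boundary, including the final one, as a Wilcoxon value. Section 10.2 is general text whose listed time points (days 1-3, day 90, years 2 and 4) omit the 6-hour assessment. Wilcoxon throughout is therefore a natural reading. But 10.2 says it covers the primary outcome and states a significance level for it, and 10.4 ties its reason for Wilcoxon to the interims. Even if Wilcoxon throughout was intended, 10.2 contradicts it and needs correcting.

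The defence is stronger on size, and four tempting inferences go too far:

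- *The plan inflates type I error.* Section 10.2 selects by distribution, not by p-value. Applied mechanically, such a rule holds error near 5%. The higher figures describe an analyst who takes whichever test is significant.
- *The 5.0% to 7.5% disagreement is the share of trials the plan would miscall.* It is how often the tests differ when both are run. With a fixed normality rule and whole-number scores, about 0 to 1.5% of verdicts change.
- *Table 5 fails if the final test is a t-test.* Its values depend on the spending function and information fractions. A final t-test at the matching nominal level holds error at about 0.05.
- *Wilcoxon is the more powerful test on the plan's figures.* It is ahead for the skewed shape and slightly behind for the other two. The plan gives a mean and SD but no shape.

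Nor do the documents say that the distribution would be judged with treatment arms visible. Section 10.1.1 calls the comparison of scores unblinded but is silent on the normality check.

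**Conclusion.** The concern holds as a specification gap and a conflict between sections. The final primary test and its threshold are not fixed, and no statement says whether 10.2 or 10.4 governs. The consequence is moderate: it matters when the result is near the boundary, and it works through analyst discretion rather than through an error in Table 5. Under free choice between the tests, type I error could reach about 5.5% to 6.6%. That is a ceiling, not an expected value, and it rests on assumed score shapes, as do the disagreement rates. The effect of a mechanical rule rests additionally on the assumed Shapiro-Wilk checks. No gain in power can be claimed for either test. The change is worth making because it is cheap and removes discretion over the decisive analysis.

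**What to change.** In both 10.2 and 10.4, state: *The primary test of the 6-hour static pain score at all three analyses is the tie-corrected Wilcoxon rank sum Z, compared with 3.36, 2.68 and 1.98. No distribution check is used to choose the test.*

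In 10.2, exempt the primary outcome from the distribution-based choice, and replace its p<0.05 criterion with the final boundary in Table 5 (|Z| ≥ 1.98, nominal p about 0.0477). Report the mean difference with a 95% confidence interval, and the t-test, as supportive results.

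The cost is a few sentences, with no change to sample size, data collection or boundaries. There is one small downside: the formal test is no longer a test of the mean difference on which 10.3 sizes the trial. That is why the mean difference and its interval should stay in the report.
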